**CLARIFICATION MEMO**

DATE: April 12, 2022  
TO: ACTG CTU Principal Investigators, CRS Leaders, and CTU/CRS Coordinators  
FROM: A5380 Protocol Team  
SUBJECT: Clarification Memo #3 for Protocol A5380

**This clarification memo (CM) does not result in a change in the protocol informed consent document.**

**The Division of AIDS does not require you to forward it to your institutional review board (IRB); however, you must follow your IRB's policies and procedures. If IRB review of clarification memos is required at your site, please submit this document for review.**

**Each site should file a copy of this CM with the protocol for reference.**

**The protocol clarification(s) contained in this memo should be implemented immediately.**

The following are clarifications (noted in bold and strikethrough) to Protocol A5380, Version 1.0, 06/07/19, titled, "A Phase II Trial of Glecaprevir/Pibrentasvir Fixed-dose Combination Treatment for Acute Hepatitis C Virus Infection (PURGE-C)."

Section 6.3.10 (Virologic Studies): The first paragraph of the fourth subsection has been revised to read:

Plasma HCV Genotype

At Step 1 screening, the HCV genotype **sample result** will be **collected, and the result will be** obtained locally (real-time) from any laboratory that has a CLIA certification or its equivalent. ONLY IF IT IS NOT AVAILABLE LOCALLY should it be done (real-time) at the designated testing laboratory (see A5380 LPC). **The participant may be enrolled with the HCV genotype result pending.**

---

---

Letter of Amendment #4 for:

**LETTER OF AMENDMENT**

DATE: October 13, 2020  
TO: ACTG CTU Principal Investigators, CRS Leaders, and CTU/CRS Coordinators  
FROM: A5380 Protocol Team  
SUBJECT: Letter of Amendment #4 for Protocol A5380

**The following information affects the A5380 study and must be forwarded to each site's institutional review board (IRB)/ethics committee (EC) as soon as possible for their information and review. This Letter of Amendment (LOA) must be approved by the IRB/EC before implementation.**

**The following information may also affect the Sample Informed Consent. The site IRB/EC is responsible for determining the process of informing participants of the contents of this LOA.**

**Upon receiving final IRB/EC and any other applicable regulatory entity approvals for this LOA, sites should implement the LOA immediately. Sites are still required to submit an LOA registration packet to the DAIDS Protocol Registration Office (PRO) at the Regulatory Support Center. Sites will receive a registration notification for the LOA once the DAIDS PRO verifies that all required LOA registration documents have been received and are complete. An LOA registration notification from the DAIDS PRO is not required prior to implementing the LOA. A copy of the LOA registration notification, along with this letter and any IRB/EC correspondence, should be retained in the site's regulatory**

file.

The main reason for this LOA is to extend the upper window for Step 2 entry to 270 days to allow for a more flexible timeline for sites and participants, given the ongoing COVID-19 pandemic.

The following are changes (noted in bold or strikethrough) to A5380, Version 1.0, 06/07/19, titled, "A Phase II Trial of Glecaprevir/Pibrentasvir Fixed-dose Combination Treatment for Acute Hepatitis C Virus Infection (PURGE-C)." These changes will be included in the next version of the A5380 protocol if it is amended at a future date. Changes that have already been made via LOA #3, dated 09/09/20, have been incorporated in the excerpted text shown below (and are no longer presented in bold or strikethrough).

1. A Protocol Signature Page (PSP) is appended for submission to the DAIDS Protocol Registration System (DPRS) as part of the LOA registration packet.
2. Section 4.3 (Step 2 Inclusion Criteria): The following revisions have been made:
  - 4.3.3 Detectable HCV RNA from the confirmatory sample (see section 6.2.4) collected within ~~112~~ **270** days of Step 2 entry.
  - 4.3.5 The following laboratory values obtained within ~~112~~ **270** days prior to Step 2 entry by any US laboratory that has a CLIA certification or its equivalent, or at any network-approved non-US laboratory that operates in accordance with GCLP and participates in appropriate external quality assurance programs.
    - INR <1.5  
NOTE: INR  $\geq 1.5$  is acceptable in participants with known hemophilia or stable on an anticoagulant regimen affecting INR at the discretion of the site PI.
    - Albumin  $\geq 3.0$  g/dL  
NOTE: For INR and albumin values, values from the virologic failure/recurrence results in Step 1 can be used and there is no need to draw additional samples.
    - For participants receiving RBV, hemoglobin  $\geq 12$  g/dL for male,  $\geq 11$  g/dL for female.
3. Section 6.2.1 (Screening Evaluations): The third paragraph has been revised to read:

For Step 1, screening evaluations to determine eligibility must be completed within 28 days prior to entry unless otherwise specified. For Step 2, participants can enter Step 2 up to ~~112~~ **270** days after the confirmatory HCV RNA sample date completed as part of Step 1.
4. Section 6.2.4 (Event-Driven Evaluations): The second paragraph of the HCV Viral Recurrence/Virologic Failure subsection has been revised to read:

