- The contact information for the Clinical Trials Specialist (CTS) needed to be updated in the roster, and the replacement of one of the statisticians. In response, the following section has been updated: cover page, roster, and study management section.
- Per DAIDS directive, changes made via CM #1, dated 10/15/19, and CM #2 (with additional revisions to reflect the current situation with the COVID-19 pandemic) have been incorporated and remain in bold/strikethrough. In response, the following sections have been updated: 4.1.5, 4.1.7, 4.1.8b, 6.2.3, 6.2.4, 6.3, 6.3.8, 6.3.9, 6.3.10.
- The upper window for Step 2 entry has been extended to 112 days from the confirmation sample. In response, the following sections have been updated: 4.3 (4.3.3, 4.3.5), 6.2.1, and 6.2.4.
- Remote consent for Step 1 and Step 2 is permitted, per local IRB guidance. In response, the following sections have been updated: 6.2.1 and the Sample Informed Consent (SIC).
- The upper window for the Step 1 week 16/SVR12 in-person follow-up visit will remain extended when the study reopens to accrual, per the COVID-19-related CM #2, dated 04/20/20 (extended upper window = +42 days). This visit remains critical for the primary outcome of the study; thus blood sample collection is required within the study window. In response, the following section has been updated: 6.2.3.
- For the Step 1 week 16/SVR12 visit, a virtual visit can be scheduled to conduct all other evaluations with a brief in-person lab visit for blood sample collection. In response, the following sections have been updated: 6.2.3, 6.3.21, and the SIC.
- For the Step 2 SVR12 visit (R+20, R+24, or R+28), the virtual visit should also be paired with a brief in-person lab visit for blood sample collection. In response, the following sections have been updated: 6.2.3, 6.3.21, and the SIC.
- In the event of possible HCV recurrence/virologic failure in Step 1, participants should return to the site within 2 weeks for collection of the HCV recurrence/virologic failure evaluations. All samples should be collected per Table 6.1-1 and stored at the site. In addition, due to COVID-19, for this visit, Liver Function Tests (LFTs), HCV RNA, HCV genotype, and HCV RAS testing, and should be drawn locally for immediate testing. In response, the following sections have been updated: 6.2.4 and the SIC.

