WHO (World Health Organization) and CDC (Centers for Disease Control and Prevention) guidelines mandate that confirmation of the initial test result must use a test that is different from the one used for the initial assessment. A reactive initial rapid test should be confirmed by either another type of rapid assay or an E/CIA that is based on a different antigen preparation and/or different test principle (e.g., indirect versus competitive), or a Western blot or a plasma HIV-1 RNA viral load.

4.3.5 The following laboratory values obtained within 56 days prior to Step 2 entry by any US laboratory that has a CLIA certification or its equivalent, or at any network-approved non-US laboratory that operates in accordance with GCLP and participates in appropriate external quality assurance programs.

- INR <1.5  
NOTE: INR  $\geq 1.5$  is acceptable in participants with known hemophilia or stable on an anticoagulant regimen affecting INR at the discretion of the site PI.
- Albumin  $\geq 3.0$  g/dL  
NOTE: For INR and albumin values, values from the virologic failure/recurrence results in Step 1 can be used and there is no need to draw additional samples.
- For participants receiving RBV, hemoglobin  $\geq 12$  g/dL for male,  $\geq 11$  g/dL for female.

4.3.6 Female participants of reproductive potential (defined as women who have not been post-menopausal for at least 24 consecutive months, i.e., who have had menses within the preceding 24 months, or women who have not undergone surgical sterilization, specifically hysterectomy and/or bilateral oophorectomy or bilateral salpingectomy) must have a negative serum or urine pregnancy test within 48 hours prior to Step 2 entry by any laboratory or clinic that has a CLIA certificate or its equivalent, or is using a POC/CLIA-waived test or at any network-approved non-US laboratory or clinic that operates in accordance with GCLP and participates in appropriate external quality assurance programs. The serum, urine or POC pregnancy test must have a sensitivity of at least 25 mIU/mL.

4.3.7 All participants must agree not to participate in a conception process (e.g., active attempt to become pregnant or to impregnate, sperm donation, in vitro fertilization).

NOTE: Female candidates who are pregnant or breastfeeding are not eligible for Step 2 of the study. A male candidate who has a pregnant female partner is also not eligible for Step 2.

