For study products provided through the study in regimens 2A-2D, a new prescription must be provided to the site pharmacist at Step 2 initiation that includes the Step number, PID, and SID. If participant is being prescribed RBV, the prescription must also include weight (kg) and CrCl.

Table 5.1.1-1: Weight-based RBV Dose

Weight (kg)	Morning Dose	Evening Dose
<75 kg	600 mg (3 tablets)	400 mg (2 tablets)
≥75 kg	600 mg (3 tablets)	600 mg (3 tablets)

The total RBV daily dose has been divided into two doses. The dose of RBV will be based on participant's weight at Step 2 entry or at confirmation visit. Changes in weight after Step 2 entry do not require a change in dose. Doses will only be changed for toxicity management.

For Step 2 participants with reduced CrCl, RBV can be dosed based on Table 5.1.1-2 below.

Table 5.1.1-2: Renal Dosing for RBV

Creatinine Clearance	RBV Dose
30-50 mL/min	Alternating doses, 200 mg (1 tablet) daily alternating with 400 mg (2 tablets) daily
Less than 30mL/min and Hemodialysis	200 mg (1 tablet) daily

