Evaluation	Re-Treatment Entry/Initiation	On-Retreatment (Weeks) R = Step 2 Entry ReTx=Retreatment					Post-Retreatment		HCV Recurrence/Virologic Failure (see Event Driven Evaluations in section 6.2.4 ) Confirmation	HIV-1 Virologic Breakthrough Confirmation (see Event-Driven Evaluations in section 6.2.4 )	Premature Study and /or Treatment Discontinuation Evaluations
		R+2 (RBV regime ns only)	R+4	R+8	R+12 (12 & 16 weeks ReTx only)	R+16 (16 weeks ReTx only)	SVR12 visit (R+20, R+24 or R+28, depending on re-treatment duration)	Only for RBV exposed (R+32, R+36 or R+40, depending on re-treatment duration)			
		See section 6.2.3 for study windows									
Evaluation of Step 2 Entry Requirements (see section 6.3.20 )	X										
Clinical Assessments (see section 6.3.7 )	X	X	X	X	X	X	X	X	X		X
Hematology, Chemistries	X	X	X	X	X	X	X		X		X
LFTs (see section 6.3.8 )									X		
Serologies (see section 6.3.8 )	X								X		
Calculated CrCl (if on RBV)	X	X	X	X	X	X					X
Pregnancy Testing (see section 6.3.8 )	X	X	X	X	X	X	X	X			X

Evaluation	Re-Treatment Entry/ Initiation	On-Retreatment (Weeks) R = Step 2 Entry ReTx=Retreatment					Post-Retreatment		HCV Recurrence/Virologic Failure (see Event Driven Evaluations in section 6.2.4 ) Confirmation	HIV-1 Virologic Breakthrough Confirmation (see Event-Driven Evaluations in section 6.2.4 )	Premature Study and /or Treatment Discontinuation Evaluations	
		R+2 (RBV regime ns only)	R+4	R+8	R+12 (12 & 16 weeks ReTx only)	R+16 (16 weeks ReTx only)	SVR12 visit (R+20, R+24 or R+28, depending on re- treatment duration)	Only for RBV exposed (R+32, R+36 or R+40, depending on re- treatment duration)				
See section 6.2.3 for study windows												
CD4+/CD8+ (for participants with HIV-1 infection)	X			X			X	X				X
Stored Plasma and PBMC (see section 6.3.9 )	X		X		X		X	X		X		X
Plasma HCV RNA (real-time, see section 6.3.10 )	X	X	X	X	X	X	X			X		X
Plasma HCV Genotype (see section 6.3.10 )										X		
Plasma HIV-1 RNA (for participants with HIV-1 infection, real-time, see section 6.3.10 )			X	X	X	X	X			X	X	X
Stored Serum for HIV-1/HCV Studies (see section 6.3.10 )		X	X	X	X		X			X	X	X

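### After LOA #4, the ribavirin hemoglobin floor in section 4.3.5 accepts values up to 270 days old, and no supplied text says the Step 2 entry value governs or must be reviewed before the first dose

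*Protocol*

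**What the plan says.** In Version 1.0, section 4.3.5 opens with one time limit for all its laboratory criteria: "The following laboratory values obtained within 56 days prior to Step 2 entry by any US laboratory". Three bullets follow: INR, albumin, and the RBV hemoglobin floor (≥12 g/dL for men, ≥11 g/dL for women). LOA #3 moved the limit to 112 days ("The upper window for Step 2 entry has been extended to 112 days from the confirmation sample"). LOA #4, the latest amendment of this section, moved it to 270. Its stated aim is to "extend the upper window for Step 2 entry to 270 days to allow for a more flexible timeline", and it gives no reason specific to hemoglobin. The bullet beginning "For participants receiving RBV, hemoglobin" has no time limit of its own.

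The note on re-use says "For INR and albumin values, values from the virologic failure/recurrence results in Step 1 can be used". Hemoglobin is not named there. Section 6.2.1, as amended, caps Step 2 entry at the same 270 "days after the confirmatory HCV RNA sample date completed as part of Step 1".

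Table 6.1-2 marks the row "Hematology, Chemistries" at Step 2 entry and, for RBV regimens, at R+2. On the RBV prescription, section 5.1.1 says: "If participant is being prescribed RBV, the prescription must also include weight (kg) and CrCl". Table 8.1.2-1 suggests, for participants without cardiac disease, reducing RBV below 10 g/dL and holding it below 8.0 g/dL.

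**The concern.** RBV causes hemolytic anemia, which section 8.1.2 expects within the first 1 to 2 weeks. A hemoglobin floor protects a participant only if the value tested against it is current. The 270-day limit was written for scheduling flexibility, and the hemoglobin bullet moved with it because it shares a lead-in with INR and albumin. If an old passing value and a current failing value are both on file, the text does not say which one decides. Nor does it say that the current one must be seen before dosing. At stake is a participant who starts a hemolytic drug at full dose while below the protocol's own floor.

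**Working it through.** The 270-day limit is a set rule with no formula behind it, so there is no stated figure to reproduce. The check is day arithmetic plus a comparison of sections.

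**1. How far the limit moved** (4.3.5 in Version 1.0, LOA #3 and LOA #4).
- Version 1.0 to LOA #3: 112/56 = 2.0-fold.
- LOA #3 to LOA #4: 270/112 = 2.4-fold, or 270 − 112 = 158 days longer.
- Overall: 270/56 = 4.8-fold. The limit is now 270/7 = 38.6 weeks.

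**2. Which older value could be in date.** Table 6.1-1 schedules hematology at Step 1 entry (day 0). Take a recurrence found at the nominal week 16 visit, day 16 × 7 = 112. The days left on that day-0 value are:
- Version 1.0: 56 − 112 = −56, already expired.
- LOA #3: 112 − 112 = 0, expiring that day.
- LOA #4: 270 − 112 = 158 days. If week 16 falls at the end of its +42-day window (112 + 42 = day 154), 270 − 154 = 116 days.

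So a hemoglobin taken before any study drug can meet the date limit for Step 2. This does not depend on a draw at the confirmatory visit.

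**3. Whether other text closes the gap.**
- Section 6.3.8 requires entry laboratory values to be recorded. It does not tie them to dosing.
- Section 6.2.2 requires Step 2 treatment to start within 72 hours of entry. Its sentence linking the first dose to completed entry evaluations is written for Step 1.
- Section 5.1.1 asks for weight and creatinine clearance on the RBV prescription, not hemoglobin.
- Section 6.3.15 has drug dispensed at Step 2 entry.
- Section 6.3.20 covers documentation of recurrence or failure and its classification. It does not mention hemoglobin.

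The protocol does write such rules for other tests. Serology results must be available before Step 2 entry (6.3.8), and the pregnancy test must fall within 48 hours before it (4.3.6). LOA #3 lets earlier hematology replace the Step 1 entry draw only if it is at most 7 days old.

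**4. The band left open** (no cardiac disease). The first numeric trigger in Table 8.1.2-1 is below 10 g/dL.
- Men: 12 − 10 = 2 g/dL (10 to <12).
- Women: 11 − 10 = 1 g/dL (10 to <11).

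Full dose, where renal dosing does not apply, is 600 + 400 = 1000 mg/day below 75 kg and 600 + 600 = 1200 mg/day from 75 kg (Table 5.1.1-1).

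**5. Next scheduled look.** R+2 has a ±3-day window: 14 − 3 = day 11 to 14 + 3 = day 17. That overlaps the period in which RBV anemia is expected.

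**6. How many.** The number on RBV is not given. Expected SVR12 failures are 44 × 0.05 = 2.2 at the assumed 95% SVR12 and 44 × 0.20 = 8.8 at 80% (2.5 and 10 with 50 enrolled). These are expected counts at two assumed rates, not upper limits. At either rate, RBV users would be fewer: failures include dropouts and re-infections (regimen 2A), and regimen 2C and the sofosbuvir-based options avoid RBV. The documents give nothing from which to estimate the share with an entry hemoglobin in the band.

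**The case against.** The strongest reply is that a current value is what the protocol means and what sites will use. Table 6.1-2 puts the evaluation of entry requirements, hematology and the RBV creatinine clearance in the same entry column. RBV cannot be prescribed without a creatinine clearance, which suggests that entry bloods are read first. LOA #3 allows local testing and pairs virtual Step 2 visits of RBV participants with an in-person draw. Section 5.4 requires review of the package insert, 4.4.11 excludes new significant illness, and the Clinical Management Committee discusses each re-treatment. The screening checklist and Manual of Procedures, neither supplied, may contain the check. All of this stands as evidence of intent and as a limit on risk. None of it states the floor, a shorter age limit or a review before dosing.

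A reader might go further and infer that a man with 12.5 g/dL at the confirmatory visit and 10.5 g/dL at Step 2 entry meets 4.3.5 and may start RBV. The documents do not support that, for two reasons. First, a confirmatory-visit hemoglobin is not clearly scheduled. Section 6.2.4 and LOA #3 list other tests there, and the single later hematology mark in the extracted Table 6.1-1 could belong to week 28 or to the recurrence visit. Second, the failing entry value also lies inside the 270 days, and nothing says that any one passing value suffices. The text is silent on the conflict; silence is not permission.

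**Conclusion.** The point holds as a minor Step 2 safety weakness. The age limit for the RBV hemoglobin is too loose for a hemolytic drug, and the supplied text neither makes the Step 2 entry value govern nor requires its review before the first RBV dose. The exposed band is 2 g/dL wide in men and 1 g/dL in women, for participants without cardiac disease. Few participants are affected and their number cannot be estimated. Harm would need a Step 1 failure, a choice of RBV over the alternatives, a fall in hemoglobin during the delay, and an entry result not acted on. R+2 hematology and Table 8.1.2-1 then limit it.

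Two further inferences should be resisted. LOA #4 did not create the gap: the missing link between entry hematology and dosing dates from Version 1.0, and the two amendments lengthened the period over which it matters. The trial's main result is not in doubt either: RBV is used only in Step 2, and the SVR12 estimate, its interval and the sample size rest on Step 1. The conclusion assumes that the unsupplied checklist and Manual of Procedures do not already contain the rule.

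**What to change.** Take the hemoglobin bullet out of the 270-day window in 4.3.5. Require instead that, for anyone to receive RBV, the Step 2 entry hematology sample (site or local commercial laboratory) shows at least 12 g/dL in men or 11 g/dL in women, and that the result is reviewed before the first RBV dose. If it does not, use regimen 2C or another option without RBV. To make this checkable, add the Step 2 entry hemoglobin to the RBV prescription line in 5.1.1, beside weight and creatinine clearance. Leave INR, albumin and HCV RNA at 270 days, so that the scheduling flexibility is kept.

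The cost is amendment wording. The sample is already scheduled at Step 2 entry, and LOA #3 already allows local testing. The downside is that RBV start, and possibly dispensing, may have to wait for the local result within the 72-hour window and may need a second contact, in an amendment meant to ease visits. The added wait is small if the creatinine clearance already comes from the entry chemistries, though the text does not say which creatinine is used. A few participants would move to a regimen without RBV.

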**LETTER OF AMENDMENT**

DATE: September 09, 2020  
TO: ACTG CTU Principal Investigators, CRS Leaders, and CTU/CRS Coordinators  
FROM: A5380 Protocol Team  
SUBJECT: Letter of Amendment #3 for Protocol A5380

**The following information affects the A5380 study and must be forwarded to each site's institutional review board (IRB)/ethics committee (EC) as soon as possible for their information and review. This Letter of Amendment (LOA) must be approved by the IRB/EC before implementation.**

**The following information may also affect the Sample Informed Consent. The site IRB/EC is responsible for determining the process of informing participants of the contents of this LOA.**

**Upon receiving final IRB/EC and any other applicable regulatory entity approvals for this LOA, sites should implement the LOA immediately. Sites are still required to submit an LOA registration packet to the DAIDS Protocol Registration Office (PRO) at the Regulatory Support Center. Sites will receive a registration notification for the LOA once the DAIDS PRO verifies that all required LOA registration documents have been received and are complete. An LOA registration notification from the DAIDS PRO is not required prior to implementing the LOA. A copy of the LOA registration notification, along with this letter and any IRB/EC correspondence, should be retained in the site's regulatory**

file.

The main reason for this LOA is to provide guidance for the resumption of study visits, in follow-up to the COVID-19-related Clarification Memo #2 (CM #2), dated 04/20/20, as US and non-US sites begin to open to research visits in the presence of the ongoing COVID-19 pandemic. A Study Monitoring Committee (SMC) review occurred on 08/17/20 for the first 10 enrolled participants who were enrolled prior to the temporary closure in March 2020 due to the COVID-19 pandemic. The outcome of the SMC review was that the study may proceed as planned. However, enrollment into the study (i.e., Step 1 entry) will remain paused until approval of this LOA #3, dated 08/26/20.

Follow-up for these 10 enrolled participants remains ongoing with modifications to allow for a mix of virtual and in-person visits. Registration for Step 2 for those already enrolled in Step 1 will resume upon approval of LOA #2, dated 08/14/20.

This LOA is being implemented for the following reasons, per team decision, unless otherwise indicated:

- The contact information for the Clinical Trials Specialist (CTS) needed to be updated in the roster, and the replacement of one of the statisticians. In response, the following section has been updated: cover page, roster, and study management section.
- Per DAIDS directive, changes made via CM #1, dated 10/15/19, and CM #2 (with additional revisions to reflect the current situation with the COVID-19 pandemic) have been incorporated and remain in bold/strikethrough. In response, the following sections have been updated: 4.1.5, 4.1.7, 4.1.8b, 6.2.3, 6.2.4, 6.3, 6.3.8, 6.3.9, 6.3.10.
- The upper window for Step 2 entry has been extended to 112 days from the confirmation sample. In response, the following sections have been updated: 4.3 (4.3.3, 4.3.5), 6.2.1, and 6.2.4.
- Remote consent for Step 1 and Step 2 is permitted, per local IRB guidance. In response, the following sections have been updated: 6.2.1 and the Sample Informed Consent (SIC).
- The upper window for the Step 1 week 16/SVR12 in-person follow-up visit will remain extended when the study reopens to accrual, per the COVID-19-related CM #2, dated 04/20/20 (extended upper window = +42 days). This visit remains critical for the primary outcome of the study; thus blood sample collection is required within the study window. In response, the following section has been updated: 6.2.3.
- For the Step 1 week 16/SVR12 visit, a virtual visit can be scheduled to conduct all other evaluations with a brief in-person lab visit for blood sample collection. In response, the following sections have been updated: 6.2.3, 6.3.21, and the SIC.
- For the Step 2 SVR12 visit (R+20, R+24, or R+28), the virtual visit should also be paired with a brief in-person lab visit for blood sample collection. In response, the following sections have been updated: 6.2.3, 6.3.21, and the SIC.
- In the event of possible HCV recurrence/virologic failure in Step 1, participants should return to the site within 2 weeks for collection of the HCV recurrence/virologic failure evaluations. All samples should be collected per Table 6.1-1 and stored at the site. In addition, due to COVID-19, for this visit, Liver Function Tests (LFTs), HCV RNA, HCV genotype, and HCV RAS testing, and should be drawn locally for immediate testing. In response, the following sections have been updated: 6.2.4 and the SIC.
- If at any point shipment of study samples is paused due to COVID-19, for the Step 1 week 16/SVR12 visit and for the Step 2 SVR12 visit, all samples should be drawn per protocol Table 6.1-1 or Table 6.1-2, respectively, and stored at the site. In addition, due to COVID-19, for this visit, an HCV RNA should also be drawn locally for immediate testing. In

response, the following section has been updated: 6.3.8.

- If hematology, chemistries, or LFTs are drawn within 7 days prior to entry (i.e., as a part of standard of care), these labs do not need to be repeated at entry. In response, the following section has been updated: 6.3.8.
- Testing required for Step 2 entry can be done at the site lab or a local commercial lab. In response, the following section has been updated: 6.3.8.
- Substance use testing has been changed to optional since this is not a clinical test and does not affect study integrity. Sites would be able to conduct the respective visit without collecting urine, given potential logistical challenges sites may face amidst the COVID-19 pandemic. In response, the following sections have been updated: 6.3.8 and the SIC.
- The methods for substance use urine testing was revised to reflect the use of either CLIA-waived point of care assays or laboratory-based methods. In response, the following section has been updated: 6.3.8.
- HCV RAS testing could be done locally. In response, the following section has been updated: 6.3.10.
- Virtual visits can be utilized for all follow-up visits (i.e., non-SVR12 visits for Step 1 and Step 2), due to COVID-19 and the participant's inability to come in for an in-person visit, or their preference not to come to the site for this visit. In response, the following sections have been updated: 6.3.21 and SIC.
- For participants on ribavirin (RBV), virtual visits for Step 2 should also be paired with a brief in-person lab visit for blood sample collection and for women, pregnancy testing. In response, the following sections have been updated: 6.3.21 and the SIC.
- Per recent template updates, a section on *Information Collected at Screening* has been added. The following section has been updated: SIC.
- Per ACTG requirements, a separate consent form has been added for storage of samples. In response, the following section has been added: Appendix III.

